### 10.6.2. Drug Interactions/Precautions

*In vitro*, CUDC-907 competitively inhibits cytochrome P450 isoenzymes CYP2C9, CYP2C19, CYP2D6 and CYP3A4 with half maximal inhibitory concentration ( $IC_{50}$ ) values of > 10, > 10, > 10, and 0.28 to 13.58  $\mu$ M, respectively. Currently, it is not known whether achievable plasma exposures of CUDC-907 in humans will approach these *in vitro* determined values. These data suggest that CUDC-907 may inhibit cytochrome P450 isoenzymes CYP2C9, CYP2C19, CYP2D6, and CYP3A4, although the clinical significance of this potential interaction has not been investigated. Subjects receiving concomitant medications metabolized by these enzymes should be monitored at the discretion of the Investigator.

Please refer to the CUDC-907 Investigator's Brochure for additional drug interaction information.

### 10.6.3. Contraception

Subjects of childbearing potential and their partners must agree to use adequate birth control throughout their participation in the study and for 30 days following the last study treatment for subjects receiving CUDC-907. Adequate contraception is defined as hormonal birth control, intrauterine device, double barrier method or total abstinence.

**NOTE:** vomiting and diarrhea may cause oral contraceptives to be ineffective.

**Table 3: Effective Methods of Contraception**

Barrier Methods	Intrauterine Device Methods	Hormonal Methods
Male condom plus spermicide plus one additional contraceptive method	Copper T	Implants
Cap plus spermicide plus one additional contraceptive method	Progesterone T 	Hormonal shot or injection
Diaphragm plus spermicide plus one additional contraceptive method	Levonorgestrel-releasing intrauterine system 	Combined pill
		Minipill
		Patch

Also considered hormonal methods of contraception.

### 10.7. Treatment Compliance

To facilitate and ascertain treatment compliance, subjects may be provided with and trained to complete a Dosing Diary, which must be returned to the clinic for review at each clinic visit.

### 10.8. Group Allocation

Based on central testing and review, subjects receiving treatment will be classified into one of the following categories for purposes of analysis: (1) Group A: *MYC* translocation+ by FISH, (2) Group B: *MYC* expression in  $\geq 40\%$  of tumor cells by IHC and/or *MYC* gene copy number gain by FISH, or (3) Group C: *MYC* translocation by FISH, and *MYC* expression in  $< 40\%$  of tumor cells by IHC, and no *MYC* gene copy number gain by FISH (Figure 1).

To facilitate early testing of *MYC* status, a separate ICF specific for *MYC* testing will be available to be signed prior to sample testing and the signing of the main ICF.

All subjects who enter into the Screening period of the study (defined as the point at which the patient signs the main ICF) will receive a unique screening number. Once all eligibility criteria are confirmed and the subject is enrolled in the study, a subject identification number will be assigned. This number will be used to identify the subject throughout the study and must be used on all study documentation related to that subject.

The study is open-label and therefore no provisions will be made for blinding.

## **11. STUDY ASSESSMENTS**

### **11.1. Screening**

The PIs at each site are responsible for maintaining a record of all screened subjects, including both those who enter the study and those who are excluded. Screening procedures performed as part of standard-of-care, in advance of signing the ICF, need not be repeated for study purposes if performed within the 28-day screening visit window.

#### **11.1.1. Patient Registration and Group Assignment**

Inclusion and exclusion criteria will be reviewed for each potential subject. By central testing, the threshold for MYC-altered status is defined as *MYC* translocation+ by FISH and/or *MYC* expression in  $\geq 40\%$  of tumor cells by IHC, and/or *MYC* gene copy number gain by FISH. Subjects will be required to submit archival (most recent available) or fresh tumor samples for central FISH and IHC testing. For subjects who enter the study with unconfirmed MYC-altered disease, fresh tumor samples are preferred.

Collection details and shipping address will be provided in the laboratory manual.

Centralized registration and group assignment for eligible subjects will be completed according to a process defined by the Sponsor (Section 10.8).

### **11.2. Safety Evaluations**

#### **11.2.1. Demographics and Medical History**

Each patient's complete medical history will be documented during Screening, including demographic information, relevant medical history, current primary cancer diagnosis, and prior cancer treatments (chemo- and immunotherapies, radiation therapy, surgeries).

#### **11.2.2. Physical Exam**

A complete physical exam will be performed at Screening, Day 1 of each cycle, and at the EOT visit. Symptom-directed physical exams are required on Days 5 and 12 of Cycle 1 and at the Post-Treatment Follow-up visits (until time of disease progression, withdrawal of consent, or any other criteria that would make the patient unable to be followed for disease response).

#### **11.2.3. Eastern Cooperative Oncology Group (ECOG) Performance Status**

ECOG performance status (scale provided in [Appendix A](#)) will be assessed at Screening, Day 1 of each Cycle, and at the EOT visit.

#### **11.2.4. International Prognostic Index (IPI)**

The IPI will be performed for each subject at Screening and at Post-Treatment Follow-up visits.

### **11.2.5. Lymphoma Assessment**

Lymphoma assessment, consisting of a physical examination, a review of the subject's current signs and symptoms, B symptoms (drenching night sweats, fevers > 101°F [38.3°C], chills, unexplained weight loss of over 10% of body mass over 6 months), and concomitant medications, will be conducted on Day 1 of every cycle, and at the EOT and Post-Treatment Follow-up visits (until time of disease progression, withdrawal of consent, or any other criteria that would make the subject unable to be followed for disease response).

### **11.2.6. Vital Signs**

Vital signs will include resting supine blood pressure, heart rate, respiratory rate, temperature, and weight (kg). Height will be measured only at Screening. Blood pressure, heart rate, respiratory rate, temperature, and weight will be measured at scheduled visits per protocol (see Schedule of Events in Section 5.1).

### **11.2.7. Clinical Laboratory Tests**

Local laboratories will perform all clinical laboratory tests and results will be provided to the Investigator. Samples will be collected at scheduled study visits before the administration of study drug unless otherwise noted, and more frequently if clinically indicated. In the event of a clinically significant  $\geq$  Grade 2 laboratory toxicity, more frequent laboratory tests should be performed until resolution or stabilization to  $\leq$  Grade 1. After Cycle 1, clinical laboratory tests may be performed within 2 business days prior to scheduled visits.

Hematology tests include complete blood count (hemoglobin, hematocrit, white blood cell [WBC], platelets) with WBC differential (total neutrophils, eosinophils, basophils, lymphocytes and monocytes).

Blood chemistry tests include sodium, potassium, magnesium, phosphate, total protein, chloride, bicarbonate, calcium, blood urea nitrogen (BUN), creatinine, uric acid, total bilirubin, alkaline phosphatase, AST, ALT, LDH, albumin, and glucose.

In addition, serum LDH will be measured during Screening.

Laboratory tests will be performed at the time points specified in the Schedule of Events (Section 5.1).

### **11.2.8. Pregnancy Testing**

A serum or urine pregnancy test will be performed for female subjects of childbearing potential at Screening, at least once per cycle prior to dosing, and at the EOT visit. The result must be negative for the subject to be enrolled in the study. A positive result observed following enrollment should be confirmed with a repeat serum pregnancy test. Pregnancy tests may be performed more frequently as clinically indicated.

### **11.2.9. Electrocardiogram**

Standard, single 12-lead ECGs at Screening and the EOT visit will include heart rate, respiratory rate, and pulse rate, QRS, and QTcF (Fridericia's formula) intervals. The Investigator will be

responsible for a thorough review of the tracings for any untoward changes from the baseline ECG for each individual subject.

During the screening ECG, if a patient has a QTcF  $\geq$  480 sec on the screening ECG, the ECG may be repeated twice (at least 24 hours apart) and the mean QTcF from the three screening ECGs must be  $<$  480 msec in order to meet eligibility criteria for trial participation.

During treatment, based on triplicate ECGs, if a patient has a mean QTcF  $\geq$  480 msec or the mean is an increase from the mean baseline (pretreatment on Day 1 of Cycle 1) QTcF of  $>$  60 msec, the ECG may be repeated 2 more times within 5 minutes. The following will be applied based on the mean of the results for all (up to 5) of the ECGs:

- Continue ECG testing hourly until the increase resolves. If not resolved in 6 hours, discontinue further treatment and refer to in-hospital care.
- If resolved in  $<$  6 hours, resume dosing but repeat the ECG schedule specified above on the next day of dosing.
  - If prolongation of QTcF meeting these criteria occurs again, discontinue further treatment and, if not resolved in 6 hours, refer to in-hospital care.
  - If QTc prolongation does not reoccur, continue treatment as specified in the protocol.

On any ECG if sustained ( $>$ 3 beats) ventricular tachycardia is detected, the patient should be referred immediately to in-hospital care.

If on any ECG, AFib is detected, the patient should be referred for appropriate cardiology care, and within no more than 6 hours after discharge from the clinic, have Holter monitoring instituted and continued for at least 48 hours. Withhold treatment until review of the Holter results:

- If AFib did not resolve within 3 hours or by the time of the start of the Holter monitoring if longer than 3 hours after discharge from the clinic, discontinue further treatment.
- If during the Holter monitoring AFib was present for  $>$  3 hours, either sustained or as accumulated AFib duration, discontinue further treatment.
- If AFib had resolved within 3 hours or by the time of the start of the Holter monitoring if longer than 3 hours after discharge from the clinic, and did not reoccur in the 48 hours of monitoring, treatment can be resumed.

- On the next day of dosing perform:
  - ECGs per the schedule outlined above.
  - Conduct Holter monitoring for 24 hours starting at least 1 hour prior to the dose.
  - Withhold the subsequent dose until review of the Holter results.
  - If AFib is again detected on ECG or of duration > 30 minutes on Holter monitoring, discontinue treatment.
  - If AFib does not reoccur, continue treatment as specified in the protocol.

#### **11.2.10. Adverse Events**

Monitoring and recording of AEs will be conducted throughout the study. Adverse events, including SAEs, will be captured on the case report forms (CRFs) from the first day of study drug dosing until the EOT visit ( $30 \pm 7$  days post the last dose of study treatment). After the EOT visit, only treatment-related SAEs will be captured. Treatment-related SAEs that are ongoing at the time of Follow-up visits should continue to be followed until resolution, return to baseline or are deemed the subject's new baseline, or until they are  $\leq$  Grade 1 (and following consultation and agreement by the Medical Monitor). Definitions, documentation, and reporting of AEs are described in detail in Section 12. Following the Follow-up visits, any SAE determined by the Investigator to be potentially related to study treatment must also be reported.

#### **11.2.11. Concomitant Medications and Other Treatments**

Information on concomitant medications and other treatments, including blood products, will be collected from 30 days prior to study drug dosing through the Follow-up visits (see Section 10.6) and will be updated at every study visit. Beginning with the Follow-up visits, only anti-cancer therapies will be documented.

### **11.3. Efficacy Evaluations**

#### **11.3.1. Baseline Disease Assessment**

Cancer staging procedures should be performed during screening according to Ann Arbor classification ([Appendix B](#)), utilizing appropriate modalities for disease assessment such as PET-CT scanning, MRI scans, bone marrow assessment, and/or other laboratory assessments. The subject's most recent tumor samples, either archived or fresh, must be sent to the central laboratory for verification of diagnosis.

For confirmation of relapsed disease (defined as PD after a CR or Cru), biopsy is preferred but FNA is acceptable. For relapse during prior treatment, biopsy/FNA reconfirmation of the lymphoma is recommended but not mandatory.

In subjects with refractory disease (defined as [a] PD during prior treatment, [b] SD after  $\geq 3$  cycles of prior treatment, or [c] PR after  $\geq 6$  cycles of prior treatment, or for stage II disease, SD after  $\geq 3$  cycles of treatment and definitive involved-field radiotherapy) with sustained PR, a confirmation biopsy for DLBCL is preferred but an FNA may be acceptable. If an FNA is inappropriate (e.g., due to biopsy inaccessibility), the Sponsor may determine eligibility

following review of imaging results and disease history. For subjects with SD or PD after prior treatment, reconfirmation of DLBCL by biopsy (preferred) or FNA is recommended but not mandatory.

### **11.3.2. Disease Response Assessments**

The Investigator and independent review committee will evaluate each subject for response to therapy according to the Revised Response Criteria for Malignant Lymphoma (Cheson et al, 2007). The independent review committee will be blinded to the investigator's assessment of response.

Efficacy assessments will be performed using CT/MRI scans of the neck, chest, abdomen, and pelvis.

Skull base-to-mid thigh PET scan is recommended but not mandated.

Contrast-enhanced MRI may be used to evaluate sites of disease that cannot be adequately imaged using CT or if contrast-enhanced CT scanning cannot be performed due to medical condition(s).

For each subject, the modality/modalities utilized at screening will be followed throughout the subject's time on study. While additional modalities may be used depending on assessment needs and disease specifics, technologies used at screening will continue to be followed at each restaging assessment to enable direct comparison with the baseline assessment.

The exploratory efficacy endpoint of ORR will be assessed according to Lugano classification (Cheson et al, 2014; Barrington et al, 2014). All subjects on active treatment will have disease response assessments (CT/MRI) performed during the last week (Day 15 – 21) of Cycles 2, 4, and 6 (each  $\pm$  3 days). If FDG-PET/CT is acquired at baseline, follow-up FDG-PET is required at Cycle 4 and at Cycle 10. PET findings with score 1 and 2 by 5-PS score are considered as PET-negative and PET findings with score 3, 4, and 5 by 5-PS score are considered as PET-positive. Subjects who continue to receive CUDC-907 after Cycle 6 will have disease response assessments (CT/MRI) performed approximately every 12 weeks  $\pm$  1 week (i.e., Cycles 10, 14, 18) until Cycle 18 in the first 12 months with scans collected through the first year, then every 24 weeks  $\pm$  2 weeks (i.e., Cycles 26, 34) until PD or death, or up to 2 years, whichever occurs first. After that, disease assessments may be performed as clinically indicated (i.e., at the discretion of the Investigator or per standard of care).

### **11.3.3. Survival Status**

Information on survival status will be collected for all subjects at the Post-Treatment Follow-up Visit time points.

## **11.4. CUDC-907 Pharmacokinetic Analyses**

Subjects will have blood samples collected for the measurement of plasma concentrations of CUDC-907 and its major metabolite(s). For all subjects, samples will be drawn 2 hours post-dose on Day 1 of Cycles 1 and 4, and on Day 1 of every other cycle thereafter (i.e., Day 1 of Cycles 6, 8, 10, etc.). In addition, for the first 50 subjects enrolled on amendment 4, blood samples will also be obtained 2 hours post-dose on Days 8 and 15 of Cycle 1. Blood samples (4

mL) will be collected using lithium heparin plasma tubes (e.g., Becton Dickinson Vacutainers Cat # 367884 or similar). One additional blood sample may be obtained at a later time point to assess for possible study drug accumulation.

A full description of sample handling procedures is included in the laboratory manual.

## **11.5. Biomarker Assessments**

### **11.5.1. Pharmacogenomic Assessments**

PAXgene® blood samples for pharmacogenomic assessment will be collected during the Screening period. Collection details and shipping address will be provided in the laboratory manual.

### **11.5.2. Plasma Biomarker Assessments**

Blood samples (20 mL) for plasma biomarker analysis will be drawn during the Screening period and on Day 1 of scheduled clinic visits per protocol (see Schedule of Events in Section 5.1). The plasma samples will be analyzed for cell-free DNA (cfDNA) and potential markers of CUDC-907 activity, such as changes in cytokine levels.

These time points may be administratively adjusted or discontinued at the discretion of the Sponsor; however, the total number of blood samples will not be increased.

Collection details and shipping address will be provided in the laboratory manual.

### **11.5.3. Tumor Biomarker Assessments**

Optional tumor samples (i.e., CNB or FNA biopsy samples for subjects with accessible lesions) may be obtained prior to the first dose and within 8 hours post-dose on Cycle 1, Day 15 through Cycle 2, Day 1. If available, archival tumor tissue samples and corresponding pathology report will also be collected. Samples will be analyzed to evaluate baseline levels and/or changes in biomarkers related to the disease and/or targeted pathways, if feasible. BCL2 and BCL6 expression and gene translocation status are among disease-related biomarkers to be tested.

Collection details and shipping address will be provided in the laboratory manual.

## **12. ADVERSE EVENTS AND SERIOUS ADVERSE EVENTS**

### **12.1. Definition of an Adverse Event**

An AE is any untoward medical occurrence associated with the use of a drug in humans, whether or not considered drug related. An AE can therefore be any unfavorable and unintended sign, symptom, or disease temporally associated with the use of a drug, without any judgment about causality. An AE can arise from any use of the drug from any route of administration, formulation, or dose, including an overdose.

An AE includes:

- An exacerbation of a pre-existing illness
- An increase in frequency or intensity of a pre-existing episodic event or condition
- A condition detected or diagnosed after study drug administration even though it may have been present prior to the start of the study

An AE does not include:

- Medical or surgical procedures (e.g., surgery, endoscopy, tooth extraction, transfusion); the condition that leads to the procedure is an AE
- Pre-existing diseases or conditions present or detected at the start of the study that do not worsen in severity or frequency
- Situations where an untoward medical occurrence has not occurred (e.g., hospitalization for elective surgery, social and/or convenience admissions)
- Overdose of either study drug or concomitant medication without any signs or symptoms

A clinical laboratory AE is any laboratory value that is considered clinically significant by the Investigator and has caused a medical intervention, dose hold, dose reduction or schedule change. Laboratory abnormalities that have not required medical intervention should not be recorded as AEs and will be captured and reported in the Laboratory section of the clinical study report.

Disease progression is a worsening of a subject's condition attributable to the disease for which the study medication is being given. This may be an increase in severity of the disease or an increase in the symptoms of the disease. New or increasing signs and symptoms related to disease progression should be reported as an AE; however, disease progression and death from disease progression should not be recorded as an AE unless death occurs within 30 days of the subject's last dose of CUDC-907.

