#### **9.3.2. Early Study Termination**

The Sponsor has the right to close the study at any time, although this should occur only after mutual consultation between the Sponsor and the Investigators. Events that may trigger early study termination include but are not limited to:

- Insufficient efficacy following interim analyses of Groups A and B.
- Significant toxicity finding.
- Insufficient bioavailability to achieve adequate study drug exposure.
- Change in development plans for the study drug.
- Slow recruitment.

A Safety Review Committee (SRC) comprised of the Medical Monitor, PI, and Sponsor representatives will be convened to review safety information on an ongoing basis for safety

surveillance. The SRC is tasked with making a recommendation to continue or stop the trial based on their assessment of available efficacy and safety information.

An initial review of safety data will be conducted by the SRC including all treated patients after the first 15 patients have completed at least one cycle of treatment. Additionally, any treatment-related deaths will be cause for pausing enrollment and initiating SRC review of all safety data.

The SRC will be tasked with making a recommendation to continue or stop the trial based on their assessment of the benefits or risks to patients based on all available safety information including:

- Grade  $\geq 3$  toxicity regardless of relationship to treatment
- Treatment discontinuation due to toxicity
- Dose reduction due to toxicity
- Death regardless of cause

Guidelines for stopping criteria are as follows:

- If a third or more of the patients have treatment-related Grade  $\geq 3$  toxicity, excluding:
  - Grade  $\geq 3$  thrombocytopenia that resolves (Grade  $< 3$ ) within 7 days
  - Grade  $\geq 3$  diarrhea that resolves (to Grade  $< 3$ ) with standard therapy
- $> 10\%$  incidence of colitis, pneumonitis, or severe hepatotoxicity
- $> 10\%$  deaths due to Grade 4 treatment-related toxicity

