### 10.5.3.3. Dose Adjustments for CUDC-907 Hematologic and Non-hematologic Toxicity

The administration of HDAC and PI3K inhibitors has been associated with predictable bone marrow suppression that is typically transient and reversible.

The administration of HDAC and PI3K inhibitors has also been associated with hyperglycemia. This hyperglycemia does not generally result in severe metabolic complications and typically resolves with therapeutic intervention. The treatment goal for glycemic control is fasting plasma glucose  $<$  160 mg/dL; while making every attempt to avoid hypoglycemia. Dose modifications of CUDC-907 are based on the severity of toxicities.

CUDC-907 dose adjustments for hematologic and non-hematologic toxicities are shown in [Table 2](#).

Table 2: CUDC-907 Dose Adjustments for Hematologic and Non-Hematologic Toxicities			
Thrombocytopenia	Grade 1 or 2 No change in dose	Grade 3 or 4 (platelets < 50,000/μL) Hold treatment until platelets ≥ 50,000/μL or baseline, then reduce dose to the next lower dose level (as applicable per Table 1 ).	Grade 4 thrombocytopenia requiring platelet transfusion Hold treatment until platelets ≥ 75,000/μL or baseline, then dose reduce to the next lower dose level (as applicable per Table 1 ).
Neutropenia	Grade 1 or 2 No change in dose	Grade 3 or 4 (ANC < 1,000/uL) Hold treatment until ANC ≥ 1000/μL, then reduce dose to the next lower dose level (as applicable per Table 1 ).	Grade 4 febrile (≥ 38.5° C) neutropenia Hold treatment until febrile neutropenia resolves and ANC ≥ 1000/μL or baseline, then dose reduce to the next lower dose level (as applicable per Table 1 ).
Anemia	Grade 1 or 2 No change in dose	Grade 3 or 4 (hemoglobin < 8 g/dL) Hold treatment until hemoglobin ≥ 10 g/dL or baseline then reduce dose to the next lower dose level (as applicable per Table 1 ).	Grade 4 anemia requiring transfusion Hold treatment until hemoglobin ≥ 10 g/dL or baseline, then dose reduce to the next lower dose level (as applicable per Table 1 ).
Recurrence of Grade 3 or 4 hematologic toxicity will be cause for a second dose modification. If the starting dose does not permit dose modification, then study drug will be discontinued.			

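### Section 12.1 gives conflicting rules on whether a laboratory abnormality that led only to a dose hold, dose reduction or schedule change is recorded as an AE

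*Combined protocol and SAP*

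**What the plan says.** Section 12.1 has two adjacent sentences on laboratory AEs. The first is the definition: the Investigator must consider the value clinically significant, and it must be one that "has caused a medical intervention, dose hold, dose reduction or schedule change". The second is an exclusion: "Laboratory abnormalities that have not required medical intervention should not be recorded as AEs". Excluded values go to the laboratory section of the study report.

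Four other parts of the protocol bear on how these sentences work in practice:

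- **Table 2, Section 10.5.3.3.** For Grade 3 or 4 thrombocytopenia, neutropenia and anemia the instruction is to hold treatment until recovery, "then reduce dose to the next lower dose level". Transfusion has its own column, for example "Grade 4 thrombocytopenia requiring platelet transfusion".
- **Section 10.5.3.1.** DLT-like events are defined as AEs. The list includes an AE that delays dosing by 7 or more consecutive days, and Grade 4 neutropenia or thrombocytopenia lasting 7 days or more.
- **Section 14.4.4.** TEAE tables are planned overall, by relationship, by severity, and for events that led to a change of treatment. Laboratory shift tables by toxicity grade are planned separately.
- **Section 9.3.2.** The first Safety Review Committee (SRC) stopping guideline begins "If a third or more of the patients have treatment-related Grade" and counts toxicity of Grade 3 or higher.

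**The concern.** Whether an event is entered as an AE is decided at the site, at the time. If the rule for entry can be read two ways, identical cytopenias may be recorded at one site and not at another, and the pooled incidence mixes the two practices. The Synopsis allows up to 65 sites.

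The events concerned are not marginal. Section 6.3.1 names thrombocytopenia and neutropenia among the drug-related Grade 3 or 4 events reported in two or more Phase 1 subjects. A safety table meant to show which TEAEs led to treatment modification could lose laboratory events whose only consequence was that modification.

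**Working it through.** The plan states no figure on this point, so there is nothing to reproduce. The check is a comparison of the texts.

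**Step 1: apply both sentences to each kind of case.** Assume throughout that the Investigator considers the value clinically significant.

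- Value led to a medical intervention (such as a transfusion), with or without a hold: AE under sentence 1; not excluded by sentence 2. They agree.
- Value led to a dose hold only: AE under sentence 1; excluded by sentence 2. They conflict.
- Value led to a dose reduction, or a hold and then a reduction, with nothing else done: AE under sentence 1; excluded by sentence 2. They conflict.
- Value led to a schedule change only: AE under sentence 1; excluded by sentence 2. They conflict.
- Value led to no action: not an AE under sentence 1; excluded by sentence 2. They agree, and the value goes to the laboratory section by design.

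The conflict is confined to the three middle cases.

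**Step 2: do those cases occur under the plan?** Yes. Table 2 prescribes hold and then reduction for Grade 3 or 4 cytopenias and treats transfusion as a separate situation. A patient managed exactly as the main column says, with no transfusion or growth factor, falls in the conflict. Hold-only cases also arise outside the blood counts: Sections 10.5.2 and 10.5.3.1 require a hold when AST, ALT, bilirubin or creatinine exceeds its retreatment limit.

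**Step 3: what depends on the AE record?**

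- TEAE incidence, and TEAEs by severity and by relationship (Section 14.4.4): directly.
- The table of TEAEs that led to treatment modification (Section 14.4.4): directly, because hold-only and reduction-only events are treatment modifications.
- DLT-like classification (Section 10.5.3.1): by definition, because these events are called AEs. A prolonged Grade 4 neutropenia handled only by a hold is on that list, yet sentence 2 says it should not be recorded.
- Laboratory shift tables (Section 14.4.4): not at all. They use graded values whatever the AE status.

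**Step 4: which reading does the rest of the protocol support?** Section 10.5.3.1 treats delay-causing events and prolonged cytopenias as AEs, and Section 14.4.4 plans a table of TEAEs that led to treatment modification. Both fit sentence 1. Neither supports a literal reading of sentence 2.

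**Step 5: the link to the SRC guideline.** Section 9.3.2 counts toxicity, not AEs, but only treatment-related toxicity. Causality assessment is described only for AEs (Section 12.2). A cytopenia kept off the AE record could therefore have a grade but no relatedness call. That is a route by which it might be missed; the protocol does not say that it would be.

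**The case against.** The best defence is that sentence 1 is the definition and sentence 2 only its loose complement, with medical intervention as shorthand for the list just given. A hold might itself be called a medical intervention. Sections 10.5.3.1 and 14.4.4 fit that reading, and it is probably what was intended. But sentence 1 lists medical intervention apart from the other three triggers, nothing announces the shorthand, and a site that follows sentence 2 as written is following the protocol. The defence identifies the right repair; it does not remove the conflict.

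It is also fair to say that the hematologic risk is not lost from the report. Shift tables will show the worst post-baseline grade. The possible under-count is in the TEAE tables.

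A reader might infer something stronger: that the choice of sentence decides whether the SRC stopping guideline is met. The documents do not support that.

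- The guideline is worded on toxicity, a term that Sections 11.2.7 and 14.4.4 apply to laboratory values without reference to AE status.
- The SRC reviews all available safety information. Grade 3 or higher toxicity regardless of relationship and dose reductions due to toxicity are separate items, so a cytopenia managed by hold and reduction can reach the committee either way.
- The criteria are guidelines for a recommendation, and they set aside Grade 3 or higher "thrombocytopenia that resolves" to below Grade 3 within 7 days.
- The first review takes place "after the first 15 patients have completed at least one cycle of treatment" but covers all treated patients, so 15 is a minimum denominator. No rate of hold-only cytopenia is given, so any example in which the tally crosses one third would be constructed.

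What remains of the SRC point is the missing relatedness call in Step 5.

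Nor is it a fault that values leading to no action are not recorded as AEs. Both sentences agree on that, and such values are deliberately sent to the laboratory section.

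**Conclusion.** The contradiction is real and can be verified from two adjacent sentences. It covers clinically significant laboratory values whose only consequence was a dose hold, dose reduction or schedule change, including Grade 3 or 4 cytopenias managed as Table 2 prescribes without other treatment. Sites following the second sentence would omit these from TEAE incidence and from the table of TEAEs that led to treatment modification, and would be inconsistent with the DLT-like definition in Section 10.5.3.1.

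The size cannot be stated. It depends on how many such events receive no transfusion, growth factor or other treatment, and on how sites read the section; the documents give neither. The conclusion rests on reading medical intervention in sentence 2 as the same item that sentence 1 lists separately.

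The effect on the SRC guideline is a possible secondary consequence only. The point should be corrected; it does not threaten the primary efficacy analysis.

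**What to change.** In Section 12.1, give the second sentence the same four conditions as the first. A laboratory abnormality would stay off the AE record only if it led to none of the following: medical intervention, dose hold, dose reduction, schedule change. This is the reading that Sections 10.5.3.1 and 14.4.4 already support. It changes recording only, and no dose or management rule.

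As a secondary clarification, Section 9.3.2 could state whether the toxicity tally is taken from AE records, from graded laboratory values, or from both, and who assigns relatedness to an event that exists only as a laboratory value. Adding laboratory values without the second part would leave a treatment-related count undefined.

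The amendment should go to sites rather than wait for the comprehensive SAP, which Section 14.4 requires only before database lock. By then AE entry and causality calls will have been made.

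The cost is one sentence in Section 12.1 and one or two in Section 9.3.2. Reported TEAE rates may be somewhat higher. Sites that have been following the second sentence would need to check earlier hold-only and reduction-only laboratory events for late entry.
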